#### 10.2. Secondary study parameter(s)

The secondary outcome parameters will be analyzed in the same way as the primary outcome. For blood pressure, body weight and clinical chemistry laboratory parameters, the average of the readings obtained at day 6 and 7 of the active and wash-out period will be used to calculate the change.

To visualize time courses of the effect in individual patients, all blood pressure and body weight readings collected throughout the study will be used.

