### Study design:

Randomized placebo-controlled double-blind cross-over N=1 trial. Eligible participants will be invited for screening. After a screening visit, eligible patients will be randomly assigned to a cross-over study consisting of two periods of 1-week treatment with dapagliflozin and two periods of 1-week treatment with placebo in random order with a 1-week wash-out period between every treatment period to avoid cross-over effects. Based on a prior study where patients were exposed to dapagliflozin 10 mg, effects of dapagliflozin on UACR, blood pressure, body weight, eGFR and plasma glucose were fully present after 1 week and returned to baseline 4 days after drug discontinuation. Hence, a 1-week treatment followed by 1 week wash-out is considered sufficient to detect treatment effects.

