### Study design

Subjects with UACR >20 mg/g (2.26 mg/mmol) with a diagnosis of type 2 diabetes who meet the inclusion criteria will be invited for screening (day -14). After the screening visit, eligible patients will proceed to a second visit (day -7). Patients will be randomly assigned to a cross-over study consisting of two periods of 1-week treatment with dapagliflozin and two periods of 1-week treatment with placebo in random order with a 1-week wash-out

period between every treatment period to avoid cross-over effects. Based on a prior study, effects of dapagliflozin on UACR, blood pressure, body weight, fasting plasma glucose and eGFR were fully present after 4 days. We will therefore ask patients to collect urine after 3, 5, 6, and 7 days. Due to day-to-day variation in UACR we are collecting multiple urine samples to increase precision and therefore collect urine at 3, 5, 6, and 7 days. We will also collect urine after 1 day to further delineate the time-course of the response to dapagliflozin and assess if the treatment effect on UACR is directly present after 1 day. Blood pressure and body weight will be recorded and blood samples will be taken at the time points described below and in the table. Overall, a 1-week treatment period is considered sufficient to detect effects on primary and secondary outcomes.

Since data collection will be performed at home using wearable devices and digital technologies, instructions will be provided during the second visit to perform data collection and study procedures at home. Data collection and measurements will be performed in each treatment period as indicated in Figure 1. Bottles with smart caps that allow real-time monitoring of adherence, blood pressure monitors, body analysis scales and study medication will be provided at the second visit. At the second visit, patients receive four numbered bottles with seven tablets in each bottle, according to their randomized treatment schema. Patients will be instructed to take the study medication once daily, in the morning.

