### Measurements:

- First morning void urine collections for measurement of UACR, sodium, potassium, urea, and osmolality will be performed at:
  - o Day -7, -3, -2 and -1
  - o Day 1, 3, 5, 6 and 7 of the active periods
  - Day 3, 5, 6 and 7 of the wash-out periods
- Ambulatory blood pressure will be measured by the patients themselves at home at:
  - o Day -7, -3, -2 and -1
  - o Day 1, 3, 6 and 7 of the active periods
  - Day 6 and 7 of the wash-out periods
- Ambulatory body weight will be measured by the patients themselves at home at:
  - Day -7, -3, -2 and -1
  - o Day 1, 3, 5, 6 and 7 of the active periods

- o Day 3, 5, 6 and 7 of the wash-out periods
- Capillary blood samples for measurement of creatinine, CRP, lipid profile, HbA1c, uric acid, glucose and NT-proBNP will be taken at:
  - Day -7 (under supervision during the second visit) and -1
  - o Day 1, 6 and 7 of the active periods
  - Day 6 and 7 of the wash-out periods

A venous blood sample will also be taken during the second visit in order to compare the clinical chemistry assessments in capillary blood with those measured in venous blood samples.

- Medication will be provided in bottles with smart caps that allow real-time monitoring of adherence.
- Dapagliflozin will be measured by a validated liquid chromatography-mass spectrometry (LC-MS/MS) analysis at day 7 of every active period in capillary blood samples to assess treatment adherence.
- Telephone calls will be made at day 3 and 6 of the first two treatment periods to assess compliance with study procedures.

Questionnaires consisting of 6 multiple choice questions and 2 open questions will be used to assess patient experience and satisfaction to guide and inform future trials and use in clinical practice.

Figure 1: Study design

	Screening visit	Run-i	n p	erio	d	Pe	erio	d 1			W	ash	-OL	it	Period 2/3/4						Wash-out			
Days	-14	-7 (2nd visit)	3	2	1	1	3	5	6	7	3	5	6	7	1	3	5	6	7	3	5	6	7	
Urine samples* (PeeSpot)		X	Х	Х	Х	Х	Х	Х	X	X	X	X	X	X	X	X	X	X	Х	X	X	Х	х	
Blood Pressure		Х	Х	Х	Х	Х	Х		Х	X			Х	Х	Х	Х		Х	Х			Х	Х	
Body weight		Х	Х	Х	Х	Х	Х	Х	Х	Х	Х	Х	Х	Х	Х	Х	Х	Х	Х	Х	Х	Х	Х	
Blood samples** (Hem-Col)		х			Х	Х			Х	Х			Х	Х	Х			Х	Х			Х	Х	
Glucose (Strips)		Х			Х	Х			Х	Х			Х	Х	Х			Х	Х			Х	Х	
Treatment adherence						Х	Х	Х	Х	Х	Х	Х	Х	Х	Х	Х	Х	Х	Х	Х	Х	Х	Х	

18

(MEMS)												
Dapagliflozin concentration (LC-MS/MS)					Х					Х		
Questionnaire												Х

\* UACR, sodium, potassium, urea, and osmolality will be measured

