### • Blood pressure measurements

The Withings® BPM Connect device will be used to monitor blood pressure. This clinically validated Wi-Fi blood pressure monitor provides medically accurate blood pressure and heart rate measurements compliant with European medical device standards. The results are within the margin of acceptance defined by the internationally recognized evaluation standard of blood pressure monitors ANSI/AAMI/ISO 81060-2:2013, EN ISO 81060-2:2014, developed by the European Society of Hypertension, British Hypertension Society and Association for the Advancement of Medical Instrumentation/American Heart Association. Both of the Withings devices will be connected with a smartphone app in order to transfer the data to Selfcare platform.

Prior to starting home blood pressure monitoring, patients will be instructed to measure their blood pressure in both arms to determine which arm should be used for future measurements. The arm that gives the higher systolic reading should be used for all future testing. Patients should place the cuff on their arm with the lower edge of the cuff approximately 2cm above the bend in their elbow. The center of the inflatable bladder should be positioned over the brachial artery on the arm's inferior surface. The forearm should be supported on a firm surface and should be at the level of the lower end of the breastbone. No tight or restrictive clothing should be worn around the arm. Patients should be seated, remain silent and be at rest for a minimum of five minutes before taking a measurement and should not have smoked, eaten, drunk a caffeinated drink or undertaken physical activity within the past thirty minutes. Patients should also avoid measuring their blood pressure with

a full bladder. Measurements should be taken in silence when the patient is relaxed, with both feet flat on the floor and their back and arm supported. Many patients automatically cross their legs, which raises their blood pressure, so it is particularly important to emphasize the need for the patient to uncross their legs when taking their blood pressure.  For each BP recording, three consecutive measurements are taken, at least 1 minute apart with the person seated. BP is recorded once daily. 

Blood and urine will be sampled with dedicated devices:

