#### 10. STATISTICAL ANALYSIS

#### 10.1. Primary study parameter(s)

The change from baseline in UACR will be calculated using the values collected at day 5, 6 and 7 of each treatment and wash-out period. Because of the skewed distribution UACR will be log-transformed before analysis. The geometric mean of these 3 values (at baseline to end of treatment) will be calculated as log(UACRend/UACRbaseline) and the geometric mean change from baseline will be determined.

The study has two cycles for two treatment periods (dapagliflozin and placebo). For calculation of response, the difference in UACR change between dapagliflozin and placebo will be calculated during the first and second cycle. To this end a linear mixed effects model with random intercepts and random slopes for treatment will be used to determine the response during each period. Fixed effects include treatment sequence, and treatment cycle. Baseline log transformed UACR may be added as covariate. Appropriate contrasts will be implemented to assess the placebo substracted response during the first and second cycle and to correlate the placebo adjusted UACR responses to dapagliflozin (fitted on the log-scale) during the two treatment periods. The variance-covariance pattern of the mixed effects model is assumed to be unstructured. If the model does not converge less stringent models will be considered.

To determine if there is within individual variation in treatment response, we will fit a linear mixed model with correlated random intercepts and random slopes for treatment and include treatment period as a fixed effect. Subsequently, we will compare (using a maximum-likelihood ratio fit test) this model against a random intercept only model with treatment and treatment period as fixed effects.

In an additional supportive analysis, we will also dichotomize response. If the placebo adjusted difference in both cycles is greater than 20% in favor of dapagliflozin (using the linear mixed effects model), the patient will meet the response definition. We will then perform a McNemar test for the proportion of concordant response (response during the two cycles or no response during

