We will repeat this analysis for the secondary outcomes such as blood pressure, body weight, and several clinical chemistry laboratory parameters, Similar to UACR, we will estimate the posterior probability of a clinically meaningful response and the overall treatment effect. clinically meaningful response as defined as:

• Blood pressure: reduction of 5 mmHg

Statistical Analysis Plan Page 12 of 13

• Body weight: reduction of 3kg

• Hba1c: reduction of 0.5%

• EGFR: reduction of 10% and 3 ml/min.

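### Blood-pressure response uses two days per week and no set time of day, although a Day 5 reading would be cheap and would cut its standard error by about 16–17%

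*Combined protocol and SAP*

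**What the plan says.** - **Schedule.** Protocol section 3 (Measurements) lists home blood pressure on Days -7, -3, -2 and -1, then "Day 1, 3, 6 and 7 of the active periods" and "Day 6 and 7 of the wash-out periods". SAP section 3.1 repeats this. Neither lists Day 5.
- **Endpoint window.** Protocol section 10.2 says that "the average of the readings obtained at day 6 and 7 of the active and wash-out period will be used" for the change in blood pressure, body weight and laboratory parameters. All pressure and weight readings also serve to plot individual time courses.
- **Primary endpoint.** Protocol section 10.1 calculates the UACR change "using the values collected at day 5, 6 and 7 of each treatment and wash-out period".
- **Onset and offset.** Protocol section 3 says that "effects of dapagliflozin on UACR, blood pressure, body weight, fasting plasma glucose and eGFR were fully present after 4 days". The protocol Summary (Study design) says that the effects "were fully present after 1 week and returned to baseline 4 days after drug discontinuation".
- **Measuring instructions.** Protocol section 8.3 sets arm, cuff, posture, rest and three consecutive measurements per recording. On timing it says only that "BP is recorded once daily". Weighing, by contrast, is preferably done in the morning before breakfast.
- **Response cut.** SAP section 5.1 lists "Blood pressure: reduction of 5 mmHg" as clinically meaningful and estimates the posterior probability of reaching it. Systolic is not named there, but systolic pressure is the listed secondary objective.

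**The concern.** The trial aims to measure response in individual patients, so the precision of each patient's estimate matters more than it would in a parallel-group comparison of means. Each placebo-subtracted pressure response combines four weekly means, and their noise adds up.

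The plan accepts the averaging argument for UACR: it takes several samples because of day-to-day variation. It gives pressure one day fewer without a reason, although the patient is already collecting urine and weighing on Day 5. (The SAP's text list omits Day 5 weight, but the SAP's own Figure 1 and the protocol include it. Day 5 urine is consistent throughout.)

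With no time of day stated, diurnal variation and a varying interval since the morning tablet can add to the day-to-day noise. At stake is how sharply the analysis can say whether a given patient's pressure fell by 5 mmHg.

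**Working it through.** **1. Reproduce the plan's count of pressure days.** The Summary states 28 days for pressure and 40 for weight.
- Pressure: 4 run-in + 4 treatment weeks × 4 + 4 wash-out weeks × 2 = 28. Agrees.
- Weight: 4 + 4 × 5 + 4 × 4 = 40. Agrees.

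The count of 28 includes a wash-out after Period 4, which is no period's baseline. Period 1 has no preceding wash-out, so its baseline must come from the run-in, where pressure is taken on Days -3, -2 and -1. The documents do not say which run-in days are used.

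**2. Windows in a patient's response.** Cycle response = (dapagliflozin end − its baseline) − (placebo end − its baseline). The two-cycle mean therefore uses eight windows: four treatment ends, three wash-out baselines and one run-in baseline. Let s be the day-to-day SD of a daily recording (the mean of its three measurements). With independent days, a window of k days has variance s²/k, and

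SE² = (1/4) × sum of the eight window variances.

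**3. Gain from Day 5 in the seven treatment and wash-out windows.**

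| Run-in window | SE now | SE with Day 5 | Reduction |
|---|---|---|---|
| 2 days, unchanged | s√[(7/2 + 1/2)/4] = 1.000s | s√[(7/3 + 1/2)/4] = 0.842s | 15.8% |
| 3 days, unchanged | s√[(7/2 + 1/3)/4] = 0.979s | s√[(7/3 + 1/3)/4] = 0.816s | 16.6% |

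The percentage does not depend on s. If all eight windows went from two to three days, the reduction would be 1 − √(2/3) = 18.4%. Part of that would come from using a third run-in day that is already measured.

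**4. Week-to-week variation.** Suppose each window also carries a week-level SD of 3 mmHg (assumed), which extra days within the week cannot reduce. For s from 5 to 12 mmHg (assumed), with all eight windows going from two to three days:
- s = 5: √(25/3 + 9) / √(25/2 + 9) = 0.90, a cut of 10%.
- s = 12: √(144/3 + 9) / √(144/2 + 9) = 0.84, a cut of 16%.

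Holding the run-in at three days before and after gives slightly less:
- s = 5: √[(8 × 25/3 + 72) / (7 × 25/2 + 25/3 + 72)] = 0.909, a cut of 9%.
- s = 12: √[(8 × 144/3 + 72) / (7 × 144/2 + 144/3 + 72)] = 0.855, a cut of about 15%.

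**5. Illustrative absolute size.** The documents give no pressure SD. Assuming s = 6, 8 or 10 mmHg, independent days and a three-day run-in baseline, the two-cycle SE falls from 5.9 to 4.9, 7.8 to 6.5, or 9.8 to 8.2 mmHg.

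**6. Time of day.** Assume s = 8 mmHg, two-day windows and an added time-of-day SD of 3 to 5 mmHg that a fixed hour would remove entirely. The two-cycle SE is √(8² + 3²) = 8.5 to √(8² + 5²) = 9.4 mmHg, against 8.0 with a fixed hour. This shows direction and rough scale only.

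**7. New count.** 4 + 4 × 5 + 3 × 3 + 1 × 2 = 35 days, seven more than now and below the 40 already used for urine and weight.

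**The case against.** **Day 5 may not be on the plateau.** The Summary says that the effects "were fully present after 1 week and returned to baseline 4 days after drug discontinuation". On that reading, averaging only the last two days is a cautious choice. The two onset statements do need reconciling. The objection is weakened because section 3 names pressure among the effects complete after 4 days, the Summary itself puts reversal at 4 days, and the primary endpoint uses Day 5 in both kinds of week.

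**The individual pressure results are not shown to be mostly noise.** A reader might infer that they are, or that a definite share of patients with no true effect will be labelled responders. The documents support neither. They give no SD, and the three measurements per recording already reduce within-session noise. A false-response rate would also assume a yes/no rule on the raw two-cycle mean. The SAP instead estimates a posterior probability and adds a mixed model, so noise appears as a less certain posterior. This objection stands.

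**Day 3 is not wasted.** It does not enter the change, but section 10.2 gives it a stated use in the time-course plots. This also stands.

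**The burden is more than seven cuff inflations.** Seven recordings mean 7 × 3 = 21 measurements, each session after five minutes' rest and with thirty minutes' restrictions on food, caffeine, smoking and activity. That is fair, but the sessions fall on mornings when patients are already collecting data.

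**Conclusion.** The point holds as a cheap improvement in precision. Nothing in the planned pressure analysis is invalid. The blood-pressure response uses one day fewer per week than the primary endpoint, without a stated reason, and its time of day is left open.

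Adding Day 5 cuts the standard error of a patient's two-cycle response by about 16–17% if days are independent. With an assumed week-to-week SD of 3 mmHg and s of 5 to 12 mmHg the cut is about 10–16%, or about 9–15% if the Period 1 baseline window is not lengthened as well. Absolute errors and the gain from a fixed hour rest on SDs that the documents do not supply. Substantial uncertainty about individual patients may remain after the change.

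Blood pressure is a secondary outcome in an unranked list. The plan's only power statement concerns UACR, so the primary analysis and N=20 do not change.

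**What to change.** 1. Add a Day 5 blood-pressure recording in the four treatment weeks and the three wash-out weeks that precede Periods 2 to 4. Day 5 in the final wash-out is optional, because it enters no response.
2. In protocol section 10.2 and SAP section 5.1, define the pressure endpoint as the mean of Days 5, 6 and 7, with Days -3, -2 and -1 as the Period 1 baseline. Name systolic pressure beside the 5 mmHg cut.
3. In protocol section 8.3 and the matching SAP text, state one consistent time of day for home readings, for example with the morning weighing, and record the time relative to the tablet. This adds no readings and is worth doing even if the sponsor keeps two days.
4. Reconcile the Summary and section 3 on when the effect is complete. If that leads the sponsor to keep Days 6 and 7 only, state why pressure is treated differently from UACR.

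Cost: schedule, instruction and endpoint wording, and seven more home recordings per patient (28 becomes 35 days).

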#### 10.3. Other study parameters

Treatment adherence will be calculated by determining the proportion of tablets taken each period. In addition, plasma dapagliflozin concentration will be assessed.

#### 10.4. Interim analysis

N/A

#### 11. ETHICAL CONSIDERATIONS

#### 11.1. Regulation statement

The study will be conducted according to the principles of the Declaration of Helsinki (Fortaleza, 2013) and in accordance with the Medical Research Involving Human Subjects Act (WMO). The Medical Ethical Committee of the University Medical Center in Groningen has to approve the study.

#### 11.2. Recruitment and consent

Patients will be recruited from the outpatient clinic of the department of Internal Medicine of the Ziekenhuisgroep Twente. Prior to their visit to the outpatient clinic, patients will be invited to participate in the study by sending a letter. In this letter, patients will find a full explanation of the study, advantages and disadvantages of participating, and contact information of the research team members working on this study. Moreover, the letter contains contact information of an independent physician, to whom subjects can address questions about the research before, during and after a study. The patients will be given 2 weeks to consider their decision and will then be asked to sign their written informed consent before they take part in the study.

#### 11.3. Objection by minors or incapacitated subjects

No minors or incapacitated adults will be included in this study.

#### 11.4. Benefits and risk assessment, group relatedness

The advantage of an N=1 study is that efficacy of the intervention is vetted for the actual participant. Since SGLT2 inhibitors are marketed in the Netherlands and recommended in patients with elevated albuminuria and type 2 diabetes mellitus, patients with diabetes who respond to dapagliflozin as determined by this study can continue to be treated with dapagliflozin. This does not yet apply to patients without diabetes. Participation in the study is on a free-will base. Patients will receive restitutions of all costs of transportation. Patients will not receive priority for treatment of other diseases in the clinic during this study. Participation in the proposed study is accompanied with only minor risks.

#### 11.5. Compensation for injury

The investigator has a liability insurance which is in accordance with article 7 of the WMO.

The sponsor University Medical Center Groningen (UMCG) has an insurance which is in accordance with the legal requirements in the Netherlands (Article 7 WMO). This insurance provides cover for damage to research subjects through injury or death caused by the study. The insurance applies to the damage that becomes apparent during the study or within 4 years after the end of the study. All patients will receive written information about this insurance.

The sponsor/investigator has a liability insurance which is in accordance with article 7, subsection 6 of the WMO.

The sponsor (also) has an insurance which is in accordance with the legal requirements in the Netherlands (Article 7 WMO and the Measure regarding Compulsory Insurance for Clinical Research in Humans of 23th June 2003). This insurance provides cover for damage to research subjects through injury or death caused by the study.

- € 650.000, (i.e. four hundred and fifty thousand Euro) for death or injury for each subject who participates in the Research;
- 2. € 5.000.000, (i.e. three million five hundred thousand Euro) for death or injury for all subjects who participate in the Research;
- 3. € 7.500.000, (i.e. five million Euro) for the total damage incurred by the organisation for all damage disclosed by scientific research for the Sponsor as 'verrichter' in the meaning of said Act in each year of insurance coverage.

The insurance applies to the damage that becomes apparent during the study or within 4 years after the end of the study.

#### 11.6. Incentives

Participation of patients in the study is a free-will decision. Patients will receive restitution of all costs for transportation. Patients do not receive priority for treatment of other diseases in the clinic during this trial.

